#### 8.1.9 Procedures for Clinical Laboratory Samples

All samples will be collected in accordance with acceptable laboratory procedures. Blood will be drawn at the start of the study and at the completion. The maximum volume of blood at any single visit is less than 10.0 mL, and the approximate total volume of blood for the study is less than 20 mL. Serum collected at the screening visit will be stored for later analysis. Blood will be redrawn at the final visit (week 14) so that pre and post immunoglobulin levels can be measured including specific IgE, and IgG4 and possibly IgG3.

The Johns Hopkins Bayview Medical Center laboratory will perform laboratory tests as indicated above. The investigator or designee is responsible for transcribing or attaching laboratory results to the CRF. The investigator will maintain a copy of the laboratory accreditation and the reference ranges for the laboratory used.

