### 8.3.5 Follow-up

Follow-up will begin the first day after the last injection and will continue until for 30 days at which time a final in-clinic visit (visit 18) will be conducted for a safety assessment and blood draw.

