#### **12.1.4 Safety Analysis**

Overall safety and tolerability will be assessed by evaluating the incidence of TEAE, laboratory tests, vital signs, and other safety variables. Treatment-emergent adverse events will be defined as any AEs, regardless of relationship to study immunotherapy, that occur on or after the first double blind immunotherapy administration date and up to 30 days after the last dose date of the double-blind immunotherapy and will be assigned to the treatment at the time of the event.

Treatment-emergent adverse events will be summarized using the full analysis set. Adverse events will be summarized using the MedDRA coding dictionary. In general, AEs will be tabulated at each of the following levels: overall summary (subject with at least 1 AE), the MedDRA system organ class (SOC) and the MedDRA preferred term (PT). Tabulations at each level of a term will present count (n) and percentage of subjects reporting any event for that term. Subjects reporting more than one occurrence for the term (level) being summarized will be counted only once and assigned to the drug assignment at time of the event.

Laboratory test variables will be summarized by active PMA or placebo assignment and study visit using descriptive statistics. Laboratory data collected from baseline and up to 7 days after a subject's last dose of study immunotherapy will be included in the analysis. Markedly abnormal laboratory values will be determined and listed by study group. The number and percentage of subjects with marked abnormality in each of the laboratory parameters will be presented.

Descriptive statistics will be used to summarize vital signs by treatment group and study visit. Vital sign data collected from baseline and up to a subject's last dose of study immunotherapy will be included in the analysis.

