## **Appendix A Schedule of Study Procedures**

Study Week:	Screen (Week 1)	Washout (Week 1-2)	Treatment (Week 3-11)	Follow-up safety assessment (Week 14)
Visit Number:	1	N/A	2-17	18
Discussion and Recruitment	X			
Informed consent	X			
Inclusion/exclusion criteria	X			
Demographics and medical history	X			
Medication history	X			
Physical examination	X			
Vital signs	X		X	
Weight and height	X			
Concomitant medications	X	X	X	X
Concurrent medical conditions	X			X
Skin Testing	X			
Blood Draw	X			X
Post-immunotherapy safety f/u				X
Administer immunotherapy/safety f/u			X	
Clinical Survey (RQLQ) and TNSS	X		X	X
Site return compliance	X		X	X
PTE assessment	X	X		
AE assessment		X	X	X

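### The 7-day laboratory window in protocol section 12.1.4 excludes the only post-baseline blood draw scheduled for subjects who complete treatment

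*Combined protocol and SAP*

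**What the plan says.** **Analysis rule.** Protocol section 12.1.4 counts laboratory tests among the components of overall safety. It states that "Laboratory test variables will be summarized by active PMA or placebo assignment and study visit using descriptive statistics", and adds a listing of markedly abnormal values and a count and percentage for each parameter. The data admitted are "Laboratory data collected from baseline and up to 7 days after" the subject's last dose. In the same section, treatment-emergent adverse events are counted to 30 days after the last dose.

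**Sampling schedule.** Section 8.1.9 states: "Blood will be drawn at the start of the study and at the completion". It places the second draw at the final visit, in week 14, and names specific IgE, IgG4 and possibly IgG3 as the assays. Appendix A marks a blood draw at visit 1 and visit 18 and none at treatment visits 2 to 17. Section 8.3.5 states: "Follow-up will begin the first day after the last injection and will continue until for 30 days", after which "a final in-clinic visit (visit 18) will be conducted for a safety assessment and blood draw". Section 8.3.4 applies the final-visit procedures, including blood, to an Early Termination Visit as well.

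**SAP.** Under Study Design, the SAP says that it follows protocol sections 12.1 to 12.3. Its lists of primary, secondary and other outcomes contain no laboratory analysis and no replacement window.

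**The concern.** The window and the schedule do not fit together. A 7-day limit suits a trial that samples during treatment or just after it. This trial takes blood before treatment and then about a month after treatment ends. For a subject who receives every injection and attends visit 18, the summary by visit reduces to the screening value, and the marked-abnormality table has nothing after baseline to count.

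The stake is a promised safety analysis that cannot be delivered as written. If the rule is followed, completers contribute no post-treatment laboratory data. If it is ignored, the analysis departs from the plan without documentation, and possibly after the blind is broken.

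**Working it through.** The check is calendar arithmetic.

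**Inputs**
- Washout: 2 weeks (protocol section 1.2).
- Treatment: 8 weeks, twice-weekly visits (section 5.1), visits 2 to 17 (Appendices A and H).
- Follow-up: 30 days after the last injection (section 8.3.5).
- Treatment weeks in Appendix A: 3 to 11.
- Post-baseline draw: visit 18, week 14 (section 8.1.9, Appendix A).
- Laboratory limit: last dose + 7 days (section 12.1.4).

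**Step 1: reproduce the plan's duration.** Visits 2 to 17 give 17 − 2 + 1 = 16 injections, and 16 / 2 = 8 weeks. The total is 2 + 8 + 30/7 = 14.3 weeks, which agrees with the stated duration of about 14 weeks. The 30-day interval is therefore consistent with a draw at about week 14.

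**Step 2: nominal gap.** 30 days from last dose to draw, against a limit of 7.

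**Step 3: gap by study week.** Assume week w covers days 7(w − 1) + 1 to 7w. Week 14 is then days 92 to 98. Eight weeks starting in week 3 end in week 10, while Appendix A runs treatment to week 11, so both are tried.

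| Last dose in | Days of that week | Smallest gap | Largest gap |
|---|---|---|---|
| Week 10 | 64–70 | 92 − 70 = 22 | 98 − 64 = 34 |
| Week 11 | 71–77 | 92 − 77 = 15 | 98 − 71 = 27 |

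Section 5.1 and the SAP also describe a six-week treatment phase. On that reading the last dose falls in week 8 (days 50 to 56) and the gap is 92 − 56 = 36 to 98 − 50 = 48 days, which is longer still.

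**Step 4: compare.** The smallest gap on any reading is 15 days, more than twice the limit. No scheduled post-baseline laboratory value from a completer is eligible.

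**Step 5: what could still enter.** An Early Termination draw within 7 days of that subject's last dose. The documents do not say how many there would be. For scale only, the recruitment allowance for drop-off is 36 − 28 = 8 subjects, or 8/36 = 22%. If all 8 left early and all had an in-window draw, the post-baseline summary would rest on those 8 and on none of the 28 completers.

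**The case against.** A reader might infer more than the documents support, in three ways.

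- **That no post-baseline laboratory data would remain at all.** This goes too far, because section 8.3.4 also lists blood at an Early Termination Visit and such a draw can fall inside the window. The exception does not rescue the rule: it leaves a summary built only on subjects who stopped early.
- **That the rule discards the post-treatment immunoglobulin samples.** The 7-day limit sits in the safety section. The immunoglobulins appear among the secondary objectives and endpoints as stored serum, to be measured later, and nothing expressly applies the safety window to them. They are, however, the only assays that section 8.1.9 names. Either section 12.1.4 covers them and excludes completers' second sample, or it covers no specified assay. Both readings call for clarification.
- **That the vital-sign cut-off at the last dose is the same error.** It is not. Visits 2 to 17 supply vital signs inside that window, and the cut-off agrees with Appendix A, which leaves vital signs unmarked at visit 18. An on-treatment window is a legitimate choice. What does conflict is section 8.3.4, which lists vital signs at the final visit, with Appendix A.

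The strongest counter-argument is that the window is secondary. With no chemistry or haematology panel and no abnormality limits specified, a marked-abnormality table would lack defined content under any window. That stands, and the fix addresses it. It is also fair that the consequences are limited: the synopsis does not name laboratory tests under safety, and none of the outcomes listed in the SAP depends on them.

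**Conclusion.** The concern holds for completers. As written, 0% of the scheduled post-baseline laboratory samples from subjects who finish treatment and attend visit 18 fall inside the window (nominally day 30 against a limit of day 7). This rests on the screening draw serving as baseline, on visit 18 taking place in week 14 or at the 30-day point, and on no unscheduled sampling. Appendix C mentions regular pregnancy tests, but they are not in the schedule and are not described as blood tests.

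The conclusion does not depend on which treatment length is right. It does not extend to Early Termination draws and does not touch the primary efficacy analysis or the adverse-event window. It is worth correcting before unblinding because the remedy is small.

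**What to change.** 1. In section 12.1.4, define the laboratory window as baseline through the visit 18 (or Early Termination) draw, whatever the exact day. Tie it to the visit rather than to a 30-day limit: visit 18 comes at the end of the 30-day follow-up with no stated tolerance, and the calendar gap can reach 34 days.
2. State that the laboratory variables are those named in section 8.1.9 (specific IgE, IgG4, possibly IgG3), summarised as change from screening to visit 18 when measured.
3. Drop the marked-abnormality listing and table unless a safety panel is specified.
4. Separately, reconcile section 8.3.4 with Appendix A on vital signs at visit 18. Also reconcile section 1.2, which allows the one-month follow-up by telephone, with the in-clinic draw in section 8.3.5. The vital-sign window itself needs no change.

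The cost is one sentence for the window and a few more for items 2 to 4, with the SAP following by reference. No samples or visits are added to the existing schedule.

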#### **12.2 Interim Analysis and Criteria for Early Termination**

No interim analyses are planned.

#### **12.3 Determination of Sample Size**

The study sample size is based upon the results of prior immunotherapy investigations undertaken by the Investigators of this study and their colleagues in the Division of Allergy & Clinical Immunology, Johns Hopkins University School of Medicine. Efficacy for immunotherapy was estimated to be 80% for treatment group and 30% for placebo. Using an error rate ( $\alpha$ ) of 0.05 and 80% Power we calculate a total sample size needed of 28 subjects. To account for drop off we will recruit up to 36 subjects.

## **13.0 QUALITY CONTROL AND QUALITY ASSURANCE**

### **13.1 Study-Site Monitoring Visits**

Monitoring visits to the study site will be made periodically during the study to ensure that all aspects of the protocol are followed. Source documents will be reviewed for verification of data recorded on the CRFs. Source documents are defined as original documents, data, and records. The investigator and institution guarantee access to source documents by the sponsor.

All aspects of the study and its documentation will be subject to review by the sponsor or designee (as long as blinding is not jeopardized), including but not limited to the Investigator's Binder, study medication, subject medical records, informed consent documentation, and review of CRFs and associated source documents. It is important that the investigator and other study personnel are available during the monitoring visits and that sufficient time is devoted to the process.

### **13.2 Protocol Deviations**

The investigator should not deviate from the protocol, except where necessary to eliminate an immediate hazard to study subjects. Should other unexpected circumstances arise that will require deviation from protocol-specified procedures, the investigator should consult with the sponsor or designee (and IRB, as required) to determine the appropriate course of action. There will be no exemptions for a prospectively approved deviation from the inclusion or exclusion criteria.

The site should document all protocol deviations in the subject's source documents. In the event of a significant deviation, the site should notify the sponsor or its designee (and IRB, as required). Significant deviations include, but are not limited to, those that involve fraud or misconduct, increase the health risk to the subject, or confound interpretation of primary study assessment. A Protocol Deviation Form should be completed by the site and signed by the sponsor or designee for any significant deviation from the protocol.

#### **Quality Assurance Audits and Regulatory Agency Inspections**

The study site also may be subject to quality assurance audits by the sponsor or designees. In this circumstance, the sponsor-designated auditor will contact the site in advance to arrange an auditing visit. The auditor may ask to visit the facilities where laboratory samples are collected, where the immunotherapy medication is stored and prepared, and any other facility used during the study. In addition, there is the possibility that this study may be inspected by regulatory agencies, including the FDA. If the study site is contacted for an inspection by a regulatory body, the sponsor should be notified immediately. The investigator and institution guarantee access for quality assurance auditors to all study documents as described in Section 13.1.

## **14.0 ETHICAL ASPECTS OF THE STUDY**

This study will be conducted with the highest respect for the individual study participants. In the study protocol, the ethical principles that have been described that have their origin in the Declaration of Helsinki, and the ICH Harmonised Tripartite Guideline for GCP. The investigators will conduct the study according to applicable Hopkins IRB requirements and align their conduct in accordance with the “Responsibilities of the Investigator” that are listed in Appendix B. The principles of Helsinki are addressed through the protocol and through appendices containing requirements for informed consent and investigator responsibilities.

### **14.1 IRB Approval**

The Johns Hopkins Hospital IRB must be constituted according to the applicable requirements. The sponsor or designee will require documentation noting the Federal Wide Assurance Number or comparable number assigned by the Department of Health and Human Services.

The sponsor or designee in conjunction with the study site investigators will supply relevant documents for submission to the Hopkins IRB for the protocol's review and approval. This protocol, a copy of the informed consent form, and, if applicable, subject recruitment materials and/or advertisements and other documents required by all applicable laws and regulations, must be submitted to the IRB for approval. The IRB's written approval of the protocol and subject informed consent must be obtained and submitted to the sponsor or designee before commencement of the study (ie, before shipment of the sponsor-supplied immunotherapy). The IRB approval must refer to the study by exact protocol title, number, and version date; identify versions of other documents (eg, informed consent form) reviewed; and state the approval date. The sponsor will supply immunotherapy solutions once the sponsor has confirmed the adequacy of site regulatory documentation and the sponsor has received permission from the competent authorities (Hopkins contracting office and Hopkins IRB) to begin the trial. Until the site receives the study immunotherapy no protocol activities, including screening may occur.

The study site must adhere to all requirements stipulated by the IRB. This may include notification to the IRB regarding protocol amendments, updates to the informed consent form, recruitment materials intended for viewing by subjects, safety reporting requirements, reports and updates regarding the ongoing review of the study at intervals specified by the IRB, and submission of the investigator's final status report to the IRB. All IRB approvals and relevant documentation for these items must be provided to the sponsor or its designee.

Subject incentives should not exert undue influence for participation. Payments to subjects must be approved by the IRB and sponsor.

### **14.2 Risks**

**Allergy Skin test** The risk of performing allergy skin testing is minimal. Serious reactions are rare. This study uses histamine and allergen for testing, which very rarely can cause serious reactions.

Most individuals experience mild to moderate itching at the site of testing that spontaneously resolves. You may feel some mild discomfort from the skin prick device itself.

**Immunotherapy** The most common side effect from allergen immunotherapy is slight swelling and discomfort at the site of the injection. This usually resolves in 1-2 days with the use of a cool pack. There is a very small chance of having a serious allergic reaction. If symptoms of a serious allergic reaction occur we would administer epinephrine and possibly other allergy medications such as antihistamines.

Some participants will receive placebo instead of active immunotherapy. These individuals may not see an improvement in their symptoms. All patients will be required to discontinue nasal steroids for two weeks prior to starting treatment. There is a risk that nasal symptoms could worsen when you stop the medication.

**Blood Draw** The most common side effect of blood draw is discomfort from the needle. This can sometimes lead to bruising of the skin. There is a very small chance of getting an infection from puncturing the skin.

**Other risks** There always exists the potential for loss of confidentiality; however, there are procedures in place to minimize this. Study information will not be associated with your private demographic information directly but linked via a numerical code only to be accessed by the study designers. However, there still remains the possibility that information about you may become known to people outside of this study.

You may get tired or bored when we are asking you questions or you are completing questionnaires. You do not have to answer any question you do not want to answer. There may be side effects and discomforts that are not yet known.

### **14.3 Benefits**

There is no direct benefit to subjects for being in this study. Taking part in this study, may help others in the future.

Subjects will be paid up to \$325 for time and effort (\$18 per visit). A parking pass will also be provided for subjects who need this. Total payment will be prorated based on the number of study visits completed and paid in two lump sums made once the study regimen begins and the rest will

---

be paid at the end of the study. Payment will be made by mailing a check within 1-2 weeks. Checks will be mailed to the address provided at the time of the consent.

#### **14.4 Subject Information, Informed Consent, and Subject Authorization**

Written consent documents will embody the elements of informed consent as described in the Declaration of Helsinki and the ICH Guidelines for GCP and will be in accordance with all applicable laws and regulations. The informed consent form describes the planned and permitted uses, transfers, and disclosures of the subject's personal and personal health information for purposes of conducting the study. The informed consent form further explains the nature of the study, its objectives, and potential risks and benefits, as well as the date informed consent is given. The informed consent form will detail the requirements of the participant and the fact that he or she is free to withdraw at any time without giving a reason and without prejudice to his or her further medical care.

The investigators in conjunction with the sponsor is responsible for the preparation, content, and IRB approval of the informed consent form. The informed consent form must be approved by both the IRB and the sponsor prior to use.

The informed consent form must be written in a language fully comprehensible to the prospective subject. It is the responsibility of the investigator to explain the detailed elements of the informed consent form to the study subject. Information should be given in both oral and written form whenever possible and in the manner deemed appropriate by the Hopkins IRB. In the event the subject is not capable of rendering adequate written informed consent, then the subject's legally acceptable representative may provide such consent for the subject in accordance with the IRB regulations.

The subject, or the subject's legally acceptable representative, must be given ample opportunity to: (1) inquire about details of the study and (2) decide whether or not to participate in the study. If the subject, or the subject's legally acceptable representative, determines he or she will participate in the study, then the informed consent form must be signed and dated by the subject, or the subject's legally acceptable representative, at the time of consent and prior to the subject entering into the study. The subject or the subject's legally acceptable representative should be instructed to sign using their legal names, not nicknames, using blue or black ballpoint ink. The investigator must also sign and date the informed consent form at the time of consent and prior to subject entering into the study; however, the sponsor may allow a designee of the investigator to sign to the extent permitted by the Hopkins IRB.

Once signed, the original informed consent form will be stored in the investigator's site file. The investigator must document the date the subject signs the informed consent in the subject's medical record. A copies of the signed informed consent form shall be given to the subject.

All revised informed consent forms must be reviewed and signed by relevant subjects or the relevant subject's legally acceptable representative in the same manner as the original informed consent. The date the revised consent was obtained should be recorded in the subject's medical record, and the subject should receive a copy of the revised informed consent form.

#### **14.5 Subject Confidentiality**

The sponsor and designees affirm and uphold the principle of the subject's right to protection against invasion of privacy. Throughout this study, a subject's source data will only be linked to the sponsor's clinical study database or documentation via a unique identification number. As permitted by all applicable laws and regulations, limited subject attributes, such as sex, age, or date of birth, and subject initials may be used to verify the subject and accuracy of the subject's unique identification number.

To comply with ICH Guidelines for GCP and to verify compliance with this protocol, the sponsor requires the investigator to permit its monitor or designee's monitor, representatives from any regulatory authority (eg, FDA) the sponsor's designated auditors, and the Hopkins IRB to review the subject's original medical records (source data or documents), including, but not limited to, laboratory test result reports, ECG reports, admission and discharge summaries for hospital admissions occurring during a subject's study participation, and autopsy reports. Access to a subject's original medical records requires the specific authorization of the subject as part of the informed consent process.

Copies of any subject source documents that are provided to the sponsor must have certain personally identifiable information removed (ie, subject name, address, and other identifier fields not collected on the subject's CRF).

